### 8.2. Endpoints

#### Primary End-points

- Proportion of viremic HCV prevalence in MSM and TGW community in Barcelona at the screening visit.
- Determination of acute cases detected by Viral load during screening visit
- HCV Seroprevalence with non-viremic status at screening visit.
- Number of days between diagnosis and treatment initiation during the study.

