#### Primary objectives

- Determine the prevalence of acute and chronic HCV infection in HIV-uninfected MSM and TGW community. Serologic prevalence will also be determined.
- Establish a fast-track circuit between Sexual Health Community centers and Hospital liver/infection diseases units to offer the possibility of starting treatment quickly after diagnosis and confirmation of HCV viremia on same day.

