#### **Phase 1:**

##### **1A. Assess the prevalence of untreated HCV infection among HIV-negative MSM and TGW.**

During the first year all clients of BCN Checkpoint (6,000-7,000) will be offered a serology test, Abbott rapid HCV test "SD BIOLINE HCV assay". It will take 5 minutes to obtain the test results.

If a positive result is obtained in serology test a Cepheid "Xpert® HCV VL Fingerstick" will be performed to identify HCV Viremic cases. The time to obtain the test result will be 60 min approximately.

In case of positive serology and positive viral load, Chemistry and Microbiology HUGTiP laboratories will be used for genotype study and hematology and chemistry.

In case of positive serology with negative viral load, standard lab serology will be also performed to confirm serology, thrown standard hospital lab circuit. If confirmation, this participant will be considered as previously HCV infection with spontaneous cure, if no treatment has been received previously (See table 1).

All participants diagnosticated with viremic HCV infection will be offered a 6 and 12 month post treatment visit to asses possible reinfections. Cepheid "Xpert® HCV VL Fingerstick" will be used as described before to evaluate reinfections. Theses visits will remain without changes during all phases of this study.

**1B.** Also, during the first year, 1.000 subjects with a previous negative "SD BIOLINE HCV assay" will be offered Cepheid "Xpert® HCV VL Fingerstick" tests to detect acute HCV infection if they fulfil at least one of the following criteriaxiii, xiv, xv, xvi, xvii, xviii, xix, xx, xxi, xxii, xxiii, xxiv:

1. Group sex with ChemSex use during last 3 months.
2. Slammering during last 3 months.
3. Fisting without gloves during last 3 months.
4. Sharing anal play toys without condoms during last 3 months.
5. Sharing sniffing roller for cocaine or other drugs during last 3 months.
6. Partner with active HCV or recently diagnosed with HCV on the last 3 months
7. PrEP use\*
8. Previous HCV Infection,
9. HIV infection recently diagnosticated.

*\*PrEP alone as unique criteria will not be considered condition to perform HCV viral load, if it is the only condition, as in our center PrEP users are screened before starting PrEP and each year with serologic screening. Also, HCV screening is performed in case of founding high liver enzymes levels in periodic blood tests performed in PrEP routine controls.*

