The participants with a previous negative "SD BIOLINE HCV assay" and a positive "Xpert® HCV VL Fingerstick" will be confirmed with the Cepheid "Xpert® HCV Viral Load". In these cases, a standard lab serology, hematology and biochemical exam will be also performed thrown standard hospital lab circuit (See table 1).

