**Table 1. Study Chronogram Phase 1**

	SCREENING	6 months Post Treatment visit*	12 months Post Treatment visit*
Informed consent	X		
Selection Criteria	X		
SD BIOLINE HCV assay	X		
Cepheid "Xpert® HCV VL Fingerstick"	a X	a X	a X
Xpert® HCV Viral Load	b X		
Routine Serology	c X		
genotype study/Hematology and biochemical analysis	d X		
Sexual behavior & demographics questionnaire	X		
PROMS questionnaire	X	X	X

- a) The participants that obtain a positive result from the SD Bioline HCV assay test will be confirmed with Cepheid "Xpert® HCV VL Fingerstick" to identify HCV viremic cases. Also first 1000 participants with a negative result from the SD Bioline HCV assay test that fulfills criteria mentioned on 1B point, will be confirmed with Cepheid "Xpert® HCV VL Fingerstick" to identify acute HCV infections. \*During V6MPTV and V12MPTM the fingerstick will be offered to all the participants with HCV infection detected during the screening visit.
- b) Acute infections with negative antibodies will be also tested with (Cepheid "Xpert® HCV Viral Load) to confirm viremic cases.
- c) In case of positive serology with negative viral load, standard lab serology will be performed to confirm serology, through standard hospital lab circuit.
- d) For the confirmed HCV Viremic cases, it will be analyzed the following parameters: blood count, Serum Creatinine, AST, ALT, GGT, alkaline phosphatases, direct and indirect Bilirubin, prothrombin time and the genotype study will be performed.

*\* Visits after 6 months and 12 months are optional and only are applicable for those patients that had been diagnosed and treated for HCV infection during the screening visit.*

After one year, a statistical analysis (interim analysis at 6 months\*) of the results will be made to determine associated factors for positive antibody test as well as for positive acute HCV test to set selection criteria for phase 2 of the study. A Draft of HCV pre-test Score will be developed with this first-year analysis and implemented during second phase.

\*Interim analysis will be used to evaluate data collection, correct incidences and to set up data analysis system. This will facilitate the results evaluation at the end of Phase 1 and it will allow to create the pre-test score to start the study Phase 2.

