## Phase 2: Targeted testing

During the second year, selected criteria from pre-test score will be used to offer clients an HCV rapid antibody test "SD BIOLINE HCV assay". Estimation of tests: 2,000-3,000. Depending on the results obtained on the first year, this analysis could change.

In addition, about 300 participants that complies the SCORE criteria founded during phase 1 for acute HCV infection, will be performed Cepheid "Xpert® HCV VL Fingerstick". On Visits V6MPT and V12MPT, screening will be performed with Cepheid "Xpert® HCV VL Fingerstick".

The goal with both detection strategies is to uncover a 3-time higher prevalence rate, according to our experience with HIV criteria obtained after evaluation of factors.

Procedures in case of positive results will be as described on first year phase. Final report will focus on proposing how the model could be replicated in other similar cities and settings.

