## 9. STATISTICAL ANALYSIS

A descriptive analysis will be conducted for the following variables: number of subjects, sociodemographic characteristics (gender, age, and partner's HCV status), sexual behavioral patterns (number of partners, drug use while having sex), PrEP use, and biological results. Results are presented in terms of incidence rate ratios (IRRs) and 95% confidence intervals (CIs) and their p-values of active HCV infections and presented as cases per 100 person-years. Depending on the type or distribution of each variable, absolute frequencies (N) and percentages (%), interquartile range (Q1- Q3), or standard deviation (SD) will be calculated. This descriptive analysis will be presented calculated for individuals separately to allow investigation of the association between groups. Categorical variables will be evaluated by Chi square test or Fisher's test, while Student's t-test or Wilcoxon test was used for continuous variables. After the first phase we will conduct a univariate analysis with all independent factors (HCV risk factors). The outcome variable will be the number of new cases of HCV and taking into account the population at risk. Factors associated with HCV infections with univariate p-value<0.1 will be entered in Poisson regression, adjusted by age and gender. A

significant level of 5% will be taken into account for all analysis performed. Descriptive statistics of demographic factors, and sexual behavior patterns and biological results will also be carried out for possible reinfections detected during follow up visits. A descriptive analysis of the patient reported outcomes will also be carried out and presented in the final report. All analyses will be carried out by means of the STATA 14.2 (StataCorp LP, College Station, TX USA).

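### Community acute and viremic HCV prevalence is promised, but antibody-negative viremia is sought only in risk-selected subsets, so the first cannot be estimated and the second is a lower bound

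*Combined protocol and SAP*

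**What the plan says.** Section 5.2 sets as a primary objective to "Determine the prevalence of acute and chronic HCV infection in HIV-uninfected MSM and TGW community". Section 8.2 turns this into "Proportion of viremic HCV prevalence in MSM and TGW community in Barcelona at the screening visit" and, as a separate primary endpoint, the determination of acute cases by viral load at screening. Neither endpoint has a stated denominator.

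Section 7.2 describes the testing:

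- **Phase 1A**, headed "Assess the prevalence of untreated HCV infection among HIV-negative MSM and TGW", offers the rapid antibody test to all clients (6,000-7,000). Every antibody-positive participant then has a fingerstick RNA test.
- **Phase 1B** looks for acute infection among antibody-negatives. Table 1, footnote a, limits it: "Also first 1000 participants with a negative result from the SD Bioline HCV assay test that fulfills criteria mentioned on 1B point". PrEP use as the only criterion does not qualify. Positive results "will be confirmed with the Cepheid" Xpert HCV Viral Load assay.
- **Phase 2** offers the antibody test to 2,000-3,000 clients chosen by the pre-test score. The RNA test for acute infection goes to "about 300 participants that complies the SCORE criteria founded during phase 1 for acute HCV infection".

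For summaries, section 9 offers "absolute frequencies (N) and percentages", together with group comparisons, incidence rate ratios per 100 person-years and a Poisson risk-factor model. It mentions a population at risk, but only for the regression, and does not define it. Section 11.4 does not list partial RNA testing among the limitations. Section 7.1 excludes people who already know that they have active HCV.

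**The concern.** The target is a whole community, but one component of the outcome is looked for only in a selected part of the people screened. An antibody-negative client without a qualifying 1B criterion has no route to an RNA test in Phase 1. A plain percentage must therefore either count such people as uninfected without a result, or leave them out and describe a group chosen for high risk.

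Prevalence is a primary objective, and section 7.2 says that the final report will propose how the model could be replicated elsewhere. Readers planning that need to know which group each figure describes. As the plan stands, a high-risk-group rate or an undercount could be reported as a community prevalence.

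**Working it through.** **Inputs.** Phase 1 size N = 6,000-7,000 (7.2). Expected seroprevalence 4.7%, 305 seropositives and 10-15 acute cases (11.5). RNA tests in antibody-negatives: 1,000 (7.2, Table 1). Phase 2: 2,000-3,000 antibody tests and about 300 RNA tests (7.2).

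**1. The plan's own count.** 0.047 × 6,500 = 305.5, which reproduces 305. The ends of the range give 0.047 × 6,000 = 282 and 0.047 × 7,000 = 329, so the plan used the midpoint.

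**2. Antibody-negatives without an RNA result, Phase 1.** This assumes that all 1,000 tests are accepted; the plan says only that they are offered.

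- N = 6,500: 6,500 − 305 = 6,195 antibody-negative; 6,195 − 1,000 = 5,195 untested; 5,195 / 6,195 = 84%.
- N = 6,000: 5,718 antibody-negative; 4,718 / 5,718 = 83%.
- N = 7,000: 6,671 antibody-negative; 5,671 / 6,671 = 85%.

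In Phase 2, about 300 of 2,000-3,000 (10-15%) are RNA-tested for acute infection, within a group already selected by score.

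**3. The acute figure under each plain denominator.** Assumption: the 10-15 cases in 11.5 are all antibody-negative and all found in 1B. Intervals are exact 95%.

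| Cases | Over 1,000 RNA-tested | Over 6,500 screened |
|---|---|---|
| 10 | 1.0% (0.48-1.83) | 0.15% (0.07-0.28) |
| 15 | 1.5% (0.84-2.46) | 0.23% (0.13-0.38) |

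The columns differ by 6,500 / 1,000 = 6.5-fold, and the plan does not say which applies.

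**4. What the true figure among those screened would depend on.** Let x be the cases found in the 1,000 tested, and let the 5,195 untested carry r times the tested rate. Antibody-negative viremic prevalence is then x(1 + 5.195r) / 6,500.

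| r (assumed) | x = 10 | x = 15 |
|---|---|---|
| 0 | 0.15% | 0.23% |
| 0.1 | 0.23% | 0.35% |
| 0.25 | 0.35% | 0.53% |
| 1 | 0.95% | 1.43% |

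Nothing in the design observes r. Clients who met a 1B criterion after the first 1,000 could be represented by those tested. Clients with no qualifying criterion had zero probability of a test, so no weight can represent them.

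**5. The viremic figure.** Among the clients antibody-tested in Phase 1, the viremic total is antibody-positive viremic, plus antibody-negative viremic detected, plus antibody-negative viremic among the untested. The plan supplies the first two. Their sum over all antibody-tested cannot exceed the true proportion by reason of the missing tests, so it is a lower bound apart from sampling error. Leaving out the 1B cases would only lower it further.

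**The case against.** The best case for the plan is that it already separates the tasks. Part 1A, offered to everyone, concerns prevalence of untreated infection, and 1B concerns detection of acute infection. Section 8.2 words the acute endpoint as a determination of cases, not as a prevalence. Antibody-positive viremia in Phase 1 is sought without risk selection, and the 84% are people who have been antibody-tested: the gap concerns antibody-negative viremia only. All of this stands, and it limits the point. It does not remove it, because the objective in 5.2 still promises acute prevalence, the viremic endpoint in 8.2 is not restricted to antibody-positives, and neither 8.2 nor section 9 states a denominator.

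A reader might infer more than the documents support:

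- **That the viremic figure is biased by a known factor.** It is not. Section 11.5 says that the viremic share of seropositives is unknown, and r is unobserved. If no antibody-negative viremia exists outside those tested, the shortfall is zero.
- **That a weighted estimator in section 9 would repair the problem.** Weighting cannot reach people with zero chance of a test; an assumption about them is unavoidable.
- **That 1B cases should be kept out of the viremic numerator.** They are confirmed viremic participants, and removing them deepens the undercount.
- **That Phase 2 will be pooled with Phase 1.** The plan does not say so. Section 11.1 schedules separate analyses, and "The goal with both detection strategies is to uncover a 3-time higher prevalence rate" implies a comparison between phases.

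**Conclusion.** The point holds and should be fixed. The design cannot yield a community acute prevalence without an assumption about antibody-negatives who are never RNA-tested, and the detected viremic proportion over all screened is a lower bound that the plan does not label as one.

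The selection rule and the missing denominators are facts of the text. The 84% (83-85% across the planned sizes) rests on the plan's 4.7% and on full acceptance of the 1,000 tests. The acute figures of 1.0-1.5% and 0.15-0.23% rest on all 10-15 cases arising in 1B. Section 5.2 gives 10-15 as the total of unknown infections and section 11.5 gives the same range for acute infections alone, so the two sections should be reconciled. The size of the shortfall in the viremic figure cannot be derived from the documents.

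**What to change.** In sections 8.2 and 9, base the primary prevalence estimates on Phase 1, report Phase 2 separately as a score-selected group, and give the following with exact 95% confidence intervals:

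- (a) antibody-positive and RNA-positive participants over all antibody-tested;
- (b) confirmed antibody-negative, RNA-positive participants over RNA-tested antibody-negatives with a qualifying 1B criterion, labelled as a high-risk-group rate and not as community acute prevalence, with the numbers offered and accepting the test;
- (c) all confirmed viremic cases, (a) plus (b), over all antibody-tested, labelled as a lower bound for viremic prevalence, optionally with a sensitivity range for antibody-negatives not RNA-tested, such as the r table above.

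Reword the acute-prevalence objective in 5.2 (and its copy in 1.7) to match (b). Since known active HCV is excluded, describe the results as previously unknown active infection among clients of the centres. Separate reporting of participants newly diagnosed with HIV is optional and probably has little effect.

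The cost is wording only, with no extra tests. The downside is a narrower headline claim, with no single community figure for acute infection.

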### **1.10. Type of population and number subjects**

Men who have sex with other men or transgender women, that are HIV negative and comes to get tested in our center or are under controls in our center.

Estimated enrollment first Phase 6000-7000 participants. Second phase 2000-3000 participants.

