### 5.2. Objectives

The primary Goal of this project is to identify HCV acute and chronic infections in HIV-uninfected MSM and TGW community and to offer them a low barrier linkage to care in the context of a fast-track circuit, offering a first visit with a specialist and starting hep C treatment in the same day after confirmation. A total of 10-15 unknown HCV infections are expected to be diagnosed during the study and to be treated. Potential risk factors for increased HCV infection rates include recreational drug use, including "chemsex", PrEP use, sex work, and several sexual behaviors. We will analyze which factors entangle an increased infection risk. This will allow us to focus and intensify screening on people with these factors while reducing the costs of continuous HCV screening in people who maintain at high risk.

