#### **Exclusion Criteria**

1. Knowledge of HIV infection from more than 7 days
2. Knowledge of active HCV infection

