### **11.5. Expected Outcome**

It is expected that HCV screening has a good acceptance in the community. It is also expected to be easy to implement both the HCV test and HCV viral load as the center is used to this kind of tests.

According to the 4.7% prevalence in the MSM community estimated by the ECDC for 2018, it is expected to find 305 positive cases of seroprevalence of HCV infection, but it is unknown how many of them will be viremic, as HCV has actively been treated with DAAs in Spain. Therefore, it will be difficult to determine the number of acute HCV infection cases to be found if HCV viral load screening is performed. Also, in our cohort this number might be influenced by the fact that the center attends a migrant community with higher rates of HCV as well as more frequent Chemsex users.

All these facts make it difficult to estimate the potential number of acute HCV cases, but we expect to find 10-15 cases of acute infections.

Implementing HCV screening among the MSM community will increase the detection of acute cases and, due to higher infectiousness, we can contribute to increase the reduction of the transmission chain among the MSM community. Creating a model that could be implemented in other community centers like BCN Checkpoint will increase HCV detection and treatment, working in line with the WHO 2030 objectives of HCV eradication.

It is also expected that acute HCV detections and partner notification create more awareness around MSM about the importance of HCV prevention.

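### The primary endpoint names viremic HCV prevalence in the community, but clients with known active HCV are excluded, so the study can estimate only previously undiagnosed viremia among tested clients

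*Combined protocol and SAP*

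**What the plan says.** The primary objective (sections 1.7 and 5.2) reads "Determine the prevalence of acute and chronic HCV infection in HIV-uninfected MSM and TGW community". The first primary endpoint (section 8.2) is "Proportion of viremic HCV prevalence in MSM and TGW community in Barcelona at the screening visit". Neither is limited to infections that were unknown before the visit.

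Section 7.1 lists as its second exclusion criterion "Knowledge of active HCV infection". People with past HCV who do not know of a current infection stay eligible.

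Two other places describe the target differently. Section 5.2 introduces the objectives with "A total of 10-15 unknown HCV infections are expected to be diagnosed during the study and to be treated". The heading of Phase 1A in section 7.2 is "Assess the prevalence of untreated HCV infection among HIV-negative MSM and TGW".

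Section 9 gives no prevalence estimator and no denominator for one, and it has no step for people excluded under criterion 2. Section 11.4, on limitations, does not mention the exclusion.

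**The concern.** A person who has been diagnosed and not yet cured has prevalent viremic HCV. Under criterion 2 that person enters neither the numerator nor the denominator. The enrolment rule therefore fits the case-finding aim of section 5.2 (unknown infections). It does not fit the objective or the endpoint. It also conflicts with the Phase 1A heading, because diagnosed people still awaiting treatment are untreated and yet are the ones kept out.

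The interpretation of the main result is at stake. In a micro-elimination project, readers will take a viremic prevalence as the remaining burden of infection. The figure this study can produce omits the diagnosed but uncured part, and the plan collects nothing that would show how large that part is.

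**Working it through.** **The plan's own figure.** There is no formal sample size. The one figure to reproduce is in section 11.5: "According to the 4.7% prevalence in the MSM community estimated by the ECDC for 2018, it is expected to find 305 positive cases". Section 1.10 gives "Estimated enrollment first Phase 6000-7000 participants", with midpoint 6,500. Then 0.047 × 6,500 = 305.5, which matches 305. The ends of the range give 0.047 × 6,000 = 282 and 0.047 × 7,000 = 329. So N = 6,500 is the plan's working denominator.

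**Inputs.**
- N = 6,500 tested (midpoint, section 1.10).
- U = viremic cases found. Section 5.2 expects 10-15 unknown infections, so U = 10 and U = 15 are used. That expectation covers the whole study. Placing all the cases in Phase 1 is a simplification, but the ratios below depend almost entirely on U and K.
- K = clients excluded only because they know they have active HCV. The documents give no value, so K is an assumption shown as a range.

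**Formulas.** The plan as written yields U/N. Viremic prevalence among the same attenders is (U + K)/(N + K). For any K > 0 the first is smaller than the second. The relative shortfall is close to K/(U + K).

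**Results for viremic prevalence.** The reported figure is 15/6,500 = 0.23% (Wilson 95% CI 0.14-0.38%) or 10/6,500 = 0.15% (0.08-0.28%).

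| K (assumed) | U = 15: (U+K)/(N+K) | Reported as share of it | U = 10: (U+K)/(N+K) | Reported as share of it |
|---|---|---|---|---|
| 0 | 15/6,500 = 0.23% | 100% | 10/6,500 = 0.15% | 100% |
| 5 | 20/6,505 = 0.31% | 75% | 15/6,505 = 0.23% | 67% |
| 10 | 25/6,510 = 0.38% | 60% | 20/6,510 = 0.31% | 50% |
| 15 | 30/6,515 = 0.46% | 50% | 25/6,515 = 0.38% | 40% |
| 30 | 45/6,530 = 0.69% | 33% | 40/6,530 = 0.61% | 25% |

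From about K = 10 the all-viremic value lies outside the study's own interval (for U = 15, 0.384% against an upper limit of 0.380%).

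**Overall serologic prevalence.** Take 305 seropositive and assume the excluded clients are all seropositive. The figure is 305/6,500 = 4.69%, against 310/6,505 = 4.77% with K = 5 and 320/6,515 = 4.91% with K = 15. The effect is downward but small.

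**Non-viremic seroprevalence** (third primary endpoint, section 8.2). Known viremic people can never be in this numerator, so the exclusion changes only the denominator. If all 15 viremic cases are among the 305 seropositives, the numerator is 305 − 15 = 290. The figure is 290/6,500 = 4.46%, against 290/6,515 = 4.45% with K = 15. It moves up by about 0.01 percentage points.

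**The case against.** Leaving out known cases is ordinary in a case-finding study. The exclusion is stated openly, and section 5.2 shows that finding unknown infections is the practical aim. This stands, and it is why the exclusion itself is not criticised. It does not change what the objective and endpoint say.

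K may be close to zero. Section 11.5 notes that HCV has been actively treated in Spain, and section 11.4 gives a treatment course of 8-12 weeks, so few clients may be known and still viremic at any time. This also stands: the documents do not show that the bias is material. Nor does the plan record anything that would show it is not.

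Three stronger readings are tempting, and the documents do not support them.
- A reader might infer that the result will be too low for Barcelona. The direction is certain only for the effect of this exclusion among attenders. Section 11.5 says the centre sees a migrant community with higher HCV rates and more frequent chemsex users. Phase 2 tests people selected by score. Both could push the figure up. RNA testing of only about 1,000 antibody-negative, higher-risk participants in Phase 1 pushes it down.
- A reader might infer that all seroprevalence results are biased downward. Overall serologic prevalence is lowered slightly, but the primary seroprevalence endpoint is the non-viremic one, which is essentially unaffected. Adding known viremic people to its numerator would be an error.
- A reader might infer that the study will be judged against the 4.7%. Section 11.5 uses that figure only to project a count, and section 9 plans no comparison with it.

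**Conclusion.** The mismatch is real and can be read directly from the text. The objective and first primary endpoint claim viremic prevalence in the community, while criterion 2 limits the study to previously undiagnosed current viremia among tested clients. Among attenders the reported figure understates viremic prevalence whenever K is at least 1, and there is no bias if K = 0.

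The size cannot be taken from the documents. With 15 cases in 6,500, the report would be 0.23% where viremic prevalence among attenders is 0.31% (K = 5) or 0.46% (K = 15). With only 10-15 infections expected, a handful of exclusions would matter. These figures rest on the assumed K and on setting the whole-study yield against the Phase 1 denominator. The net error against all of Barcelona remains unknown. Confidence is high for the mismatch in wording; the magnitude is illustrative only.

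**What to change.** 1. In sections 1.7, 5.2 and 8.2, rename the objective and endpoint *prevalence of previously undiagnosed viremic HCV among tested HIV-negative MSM/TGW clients*. Inclusion criterion 3 also admits clients diagnosed with HIV in the previous 7 days, so state whether they are counted in or shown apart.
2. Align the term for untreated infection in the Phase 1A heading of section 7.2 with that name.
3. At the selection-criteria check already scheduled at screening (Tables 1 and 2), keep an anonymous count of clients excluded only for known active HCV who would otherwise have taken part.
4. In section 9, define U/N as the estimator, report K beside it by phase, and give (U + K)/(N + K) as a sensitivity figure for viremic prevalence only. Make no add-back for non-viremic seroprevalence.

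The cost is wording in a few sections and one tally at an existing step. The downside is that known-active status is self-reported and not confirmed by RNA. K may also not come from exactly the same consenting population as N, so counting people who would have refused anyway would overstate the total. The sensitivity figure is therefore approximate and should be labelled so.

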## 7. STUDY DESIGN

### 7.1. *Study population: Selection criteria*

#### **Inclusion Criteria**

1. All BCN Checkpoint and BCN PreP-Point clients.
2. 18 years and older.
3. HIV uninfected or diagnosed in the center in the last 7 days prior to the study inclusion.
4. Men that have sex with men or transgender women.
5. Signature of written consent form.
6. Ability to comply with the requirements of the study protocol.

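### The first primary endpoint is labelled as prevalence in Barcelona's MSM and TGW community, but the sample is eligible clients of two linked centers, so it does not represent that community and the direction of the bias is unknown

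*Combined protocol and SAP*

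**What the plan says.** The first primary endpoint in section 8.2 is "Proportion of viremic HCV prevalence in MSM and TGW community in Barcelona at the screening visit". The prevalence objective in 1.7 and 5.2 also refers to the MSM and TGW community, there restricted to HIV-uninfected people.

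The sampling frame is narrower. The first inclusion criterion in 7.1 is "All BCN Checkpoint and BCN PreP-Point clients", and 1.10 describes people "that are HIV negative and comes to get tested in our center or are under controls in our center". The exclusion criteria remove anyone with "Knowledge of active HCV infection" or "Knowledge of HIV infection from more than 7 days".

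Section 11.5 comments on the clientele, saying that "the center attends a migrant community with higher rates of HCV as well as more frequent Chemsex users". The statement is hedged ("in our cohort this number might be influenced by the fact") and follows a sentence about the number of acute cases.

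Section 9 lists gender, age, partner's HCV status, number of partners, drug use during sex and PrEP use among the variables to be described. It does not mention center or origin, and it has no weighting or standardisation. Section 11.4 covers recruitment, under-reported risk behaviour, distance to the hospital, partner notification and migrants' access to treatment. It does not say that clients may differ from the wider community.

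**The concern.** People who choose to attend two linked sexual-health services, one of them a PrEP service, are not a sample of a city's MSM and TGW community. The plan says its clientele includes groups with more HCV risk, and its own eligibility rules then remove people known to be viremic. The endpoint label mentions neither.

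At stake is what the primary result means. A reader of the final report would take the figure as Barcelona prevalence. Enrolling more clients narrows the interval but does not bring the estimate closer to the city's value.

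**Working it through.** **1. The plan's own figure.** Section 11.5 expects 305 seropositive cases at 4.7%. With the midpoint of 6,000–7,000 participants, 0.047 × 6,500 = 305.5, so the figure reproduces. The ends of the range give 282 and 329. This is seroprevalence, whereas the endpoint at issue is viremic prevalence.

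**2. Forces on the viremic estimate.**
- Upward: migrants with higher HCV rates and more frequent chemsex users among clients (11.5).
- Downward: known active HCV is excluded (7.1).
- Downward: PrEP clients already have serology at PrEP start and yearly (7.2, Phase 1, note to 1B).
- Downward: viral load in antibody-negative clients is limited to 1,000 people meeting a risk criterion (7.2, Phase 1, 1B). At the midpoint, 6,500 − 305 = 6,195 would be antibody-negative, and 6,195 − 1,000 = 5,195 of them (84%) would have no viral load.

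**3. Can the sign be determined?** The documents give no share of high-risk people among clients or in the city, no prevalence ratio, and no share of viremic people who know their status. The following inputs are therefore assumptions. Let s_c and s_m be the high-risk share among clients and in the community, RR the prevalence ratio for high-risk people, and k the share of viremic people excluded because their infection is known. Then

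client/community ratio = [1 + s_c(RR − 1)] / [1 + s_m(RR − 1)] × (1 − k).

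| s_c, s_m, RR | k = 0 | k = 0.2 | k = 0.5 |
|---|---|---|---|
| 30%, 20%, 2 | 1.3/1.2 = 1.08 | 0.87 | 0.54 |
| 50%, 20%, 3 | 2.0/1.4 = 1.43 | 1.14 | 0.71 |
| 60%, 10%, 5 | 3.4/1.4 = 2.43 | 1.94 | 1.21 |

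The grid falls on both sides of 1. It leaves out the PrEP-screening and viral-load limits, which would lower it further. It also takes the target as HIV-uninfected people, as the objective does. The endpoint label does not carry that restriction. If HIV-positive people belonged to the target (assumed 15% of the community with RR 5), every ratio would be divided by 1 + 0.15 × 4 = 1.6, and the last column would become 0.34, 0.45 and 0.76.

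**4. Combining phases.** Phase 2 tests people selected by the pre-test score and aims at a threefold higher prevalence (7.2, Phase 2). If that goal were met, combined prevalence relative to Phase 1 would be (N1 + 3·N2)/(N1 + N2):
- 7,000 and 2,000: 13,000/9,000 = 1.44
- 6,500 and 2,500: 14,000/9,000 = 1.56
- 6,000 and 3,000: 15,000/9,000 = 1.67

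This inflation would come from score selection, not from who attends the centers.

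**5. Precision.** The plan expects 10–15 infections, called unknown infections in 5.2 and acute infections in 11.5. If about that many viremic cases arose among 6,500 people, prevalence would be 0.15–0.23%. The exact 95% interval is 0.07–0.28% for 10 cases and 0.13–0.38% for 15. For seroprevalence, 305/6,500 gives 4.19–5.23%. Strata can therefore be informative for seroprevalence but hardly for viremia.

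**The case against.** Sections 1.10 and 7.1 state openly that participants are clients of the centers, so a careful reader could see what was sampled. On that view the point is only about wording. Section 9 also analyses drug use during sex and PrEP use as risk factors and plans comparisons between groups, so chemsex is largely covered. Both observations are fair, and the second leaves center and origin as the main gaps. Neither changes the endpoint label, which is what the primary result will be reported under.

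A reader might infer more than the documents support, in three ways.
- **That the figure overstates Barcelona prevalence.** Section 11.5 says only that a number might be influenced, in a passage on acute cases, and never compares clients with the city's community. The exclusions and testing limits act in the opposite direction.
- **That a prevalence figure will be carried to other cities.** Section 7.2 says "Final report will focus on proposing how the model could be replicated in other similar cities and settings". The hypothesis in 5.1 shows that this refers to the testing and linkage-to-care model.
- **That section 9 commits to one figure pooled over centers and phases.** It does not say so, but it does not specify reporting by center or phase either.

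**Conclusion.** The mislabelling stands. The first primary endpoint names a community that the design does not sample, and neither the analysis nor the limitations section deals with this. The estimate is valid, at most, for eligible clients of the two centers.

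The net direction and size of the bias relative to the city are unknown. The range of 0.54 to 2.43 rests wholly on assumed inputs and shows only that either sign is possible. The one figure tied to the plan's own numbers is the inflation of about 1.4 to 1.7 times from combining phases, and it is conditional on Phase 2 reaching its threefold goal and on the phases being combined. Recruitment and testing are unaffected.

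**What to change.** - **8.2, 1.7 and 5.2:** reword the endpoint and the prevalence objective to prevalence among eligible clients of BCN Checkpoint and BCN PrEP·Point, meaning HIV-uninfected or newly diagnosed and without known active HCV.
- **Phases:** take the prevalence estimate from Phase 1 only and report the score-selected Phase 2 separately.
- **Section 9:** give exact 95% confidence intervals for viremic prevalence and seroprevalence overall. For seroprevalence, add a table by center, chemsex use and, where recorded, origin. Label any strata for viremic prevalence as descriptive.
- **11.4:** add clientele selection as a limitation, naming the forces in both directions.
- **Final report:** do not present the figure as Barcelona community prevalence.

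The cost is wording plus one table. Whether origin is collected cannot be checked here, because the questionnaire (Appendix 2) is a separate document. The downside is a narrower claim and wide intervals in small strata.
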